**Pregnancy:**

In rare cases, pregnancy might occur in a NIS. Once a patient has been enrolled in the study and has taken study medication, the investigator must report any drug exposure during pregnancy in a study participant within 7 days by means of Part A of the Pregnancy Monitoring Form to the sponsor's unique entry point.

The outcome of the pregnancy associated with the drug exposure during pregnancy must be followed up and reported to the sponsor's unique entry point on the Pregnancy Monitoring Form (Part B).

The ISF will contain the Pregnancy Monitoring Form (Part A and B). As pregnancy itself is not to be reported as an AE, in the absence of an accompanying serious ADR and/or AESI, only the Pregnancy Monitoring Form and not the NIS AE form is to be completed. If there is a serious ADR and/or AESI associated with the pregnancy a NIS AE form must be completed in addition.

The following must be collected by the investigator in the (e)CRF from signing the informed consent onwards until the end of the study:

all adverse drug reactions (ADRs) (serious and non-serious),  
all AEs with fatal outcome,  
all AESIs

All ADRs and AESIs, including those persisting after study completion must be followed up until they are resolved, have been sufficiently characterized, or no further information can be obtained.

Expedited Reporting of AEs and Drug Exposure during Pregnancy to BI Pharmacovigilance

The following must be reported by the investigator on the NIS AE form and/or Pregnancy Monitoring Form from signing the informed consent onwards until the end of the study and provide o BI unique entry point:

All serious ADRs associated with the studied medical product nintedanib	immediately within 24 hours
All AEs with fatal outcome in patients exposed to studied medical product nintedanib	immediately within 24 hours
All protocol specified AESIs	Immediately within 24 hours
All non-serious ADRs associated with the studied medical product nintedanib	7 calendar days
Drug exposure during pregnancy	7 calendar days

The same timelines apply if follow-up information becomes available for the respective events. In specific occasions the Investigator could inform the Sponsor upfront via telephone. This does not replace the requirement to complete and fax the NIS AE form.

Information required

For each reportable adverse event, the investigator should provide the information requested on the appropriate (e)CRF page and the NIS AE form.

### **11.3 REPORTING TO HEALTH AUTHORITIES**

Adverse event reporting to regulatory agencies will be done by the Marketing Authorization Holder (MAH) according to local and international regulatory requirements.

## **12. PLANS FOR DISSEMINATING AND COMMUNICATING STUDY RESULTS**

Results of this non-interventional study will be disclosed on encepp.eu and clinicaltrials.gov and a study specific publication plan will be developed to describe planned publications.

The rights of the investigator and of the sponsor with regard to publication of the results of this study are described in the investigator contract. As a general rule, no study results should be published prior to finalization of the Study Report.

## **ANNEX 1. LIST OF STAND-ALONE DOCUMENTS**

*None*

### **ANNEX 3. ADDITIONAL INFORMATION**

Not applicable

## LIST OF ABBREVIATIONS

ADR	Adverse drug reaction
AE	Adverse event
AESI	Adverse event of special interest
BI	Boehringer Ingelheim
CI	Confidence interval
Covid-19	Coronavirus disease 2019
CRF	Case report form
DLCO	Diffusing capacity of the lungs for carbon monoxide
FVC	Forced vital capacity
HRCT	High-resolution computer tomography
ICH	International conference on harmonisation
ILD	Interstitial lung disease
IPF	Idiopathic pulmonary fibrosis
IQR	Interquartile range
L-PF	Living with pulmonary fibrosis questionnaire
LPI	Last patient in
MedDRA	Medical dictionary for regulatory activities
MMRM	Mixed effect Model for Repeated Measures
NIS	Non-interventional study
PF-ILD	Progressive fibrosing interstitial lung disease
PPS	Per protocol set
PRO	Patient-reported outcome
PT	MedDRA preferred term
RCT	Randomized controlled trial
REML	Restricted maximum likelihood
RWE	Real-world evidence
RWE CoE	Real-world evidence analytics centre of excellence
SAE	Serious adverse event
SAP	Statistical analysis plan
SAS	Statistical analysis system
SEAP	Statistical and epidemiological analysis plan
SmPC	Summary of product characteristics
SOC	MedDRA system organ class
SOP	Standard operating procedure
TDM	Trial Data Manager
TEAE	Treatment-emergent adverse event
TLF	Table, list and figures
TM Epi	Team Member Epidemiology
TS	Treated set
TSTAT	Trial statistician

## 3. PURPOSE AND SCOPE

As per ICH E9 (International Conference on Harmonisation), the purpose of this document is to provide a more technical and detailed elaboration of the principal features of the analysis described in the protocol, and to include detailed procedures for executing the statistical analysis of the primary and secondary variables and other data.

This Statistical and Epidemiological Analysis Plan (SEAP) assumes familiarity with the Observational plan, including Protocol Amendments. In particular, the SEAP is based on the planned analysis specification as written in Observational plan Section 9.7 “Data Analysis”. Therefore, SEAP readers may consult the Observational plan for more background information on the study, e.g., on study objectives, study design and population, definition of measurements and variables, planning of sample size, randomization.

SAS® Version 9.4 (or later version) will be used for all standard analyses.

## 4. AMENDMENTS AND UPDATES

This amendment encompasses changes related to the analysis populations.

Patients in the treated set needed to sign the written informed consent form. The analysis on the per protocol set was not required in the observational plan and was added post hoc in order to identify a treatment effect which would occur under optimal conditions. Patients in the per protocol set needed to meet all inclusion and exclusion criteria and must not have violated any important protocol deviations.

## 5. RESEARCH QUESTION AND OBJECTIVE

### 5.1 PRIMARY OBJECTIVE

The primary objective of this observational study is to investigate the correlation between changes from baseline at 52 weeks in FVC [% pred.] and changes from baseline at 52 weeks in dyspnea score [points] or cough score [points] as measured with the L-PF questionnaire over 52 weeks of nintedanib treatment in patients suffering from chronic fibrosing ILD with a progressive phenotype (excluding IPF):

- Correlation between change from baseline to week 52 in FVC [% pred.] and change from baseline to week 52 in dyspnea symptom score
- Correlation between change from baseline to week 52 in FVC [% pred.] and change from baseline to week 52 in cough symptom score

### 5.2 SECONDARY OBJECTIVE

- Correlation between change from baseline to week 52 in FVC [mL] and change from baseline to week 52 in dyspnea symptom score
- Correlation between change from baseline to week 52 in FVC [mL] and change from baseline to week 52 in cough symptom score
- Absolute change from baseline in L-PF cough symptom score at week 52
- Absolute change from baseline in L-PF dyspnea symptom score at week 52

Primary and secondary objectives will be analyzed for the Treated Set.

### 5.3 ADDITIONAL OBJECTIVE

Collection of serious and non-serious adverse drug reactions and fatal adverse effects during the whole NIS (52 weeks) and reporting according to relevant SOP.

This is the first RWE study in patients suffering from chronic fibrosing ILD with a progressive phenotype in Germany being treated with nintedanib. In addition, the German healthcare system is currently strongly supporting all necessary activities to fight the global Covid-19 pandemic with possible effects on the conduct of this study. In order to be able to identify and counteract possible restrictions due to these circumstances, a descriptive snapshot analysis is planned at the time of Last Patient In (LPI) in this study.

## 6. RESEARCH METHODS

### 6.1 STUDY DESIGN

This is a single-arm, open-label observational cohort study according to §4, section 23 and §67, section 6 German Medicines Act (NIS): All included chronic fibrosing ILD with a progressive phenotype patients will receive treatment with nintedanib for approximately 52 weeks. NIS based on newly collected data.

For more details on study design please see section 9.1 of the Study Protocol.

### 6.2 SETTING

In this NIS, data on the effect of a nintedanib in chronic fibrosing ILD with progressive phenotype in about 100 patients will be collected in routine clinical practice by ca. 20 specialists, experienced in treating ILD patients, (e. g. pulmonologists and rheumatologists) throughout Germany. Each investigator will include ca. 5 consecutive patients for whom the physician had decided on a nintedanib treatment before.

Per definition, non-interventional studies do not include any randomization. In this study, there will be no procedure outside routine clinical practice. Patients will be recruited for this study only after a physician's therapeutic decision to treat the individual patient with nintedanib.

For ethical and/or medical reasons, patients with contraindications to nintedanib according to SmPC, including pregnant or lactating women, current cancer patients, patients not willing to consent and patients being spouse or lateral relatives to the second degree or economically dependent from the investigator will be excluded.

All calculations for this study, including statistics and patient numbers, are based on the randomized clinical trial INBUILD. In order to be able to duplicate the most crucial design features, in this study nintedanib will solely be tested as a first and only antifibrotic treatment in PF-ILD patients, as it was in INBUILD. Therefore, in accordance with INBUILD trial design, patients must not have used or use any antifibrotic before or during this observational study apart from nintedanib.

This study is planned to observe patients for 12 months. Therefore, patients with a life expectancy of 12 months or less should not be included. As acute exacerbations severely impact life expectancy, patients with acute ILD exacerbations should not be included in the study.

Patients must not participate in a parallel interventional clinical trial for not to interfere with the study aims and outcomes.

The impact of excluding those patients seems low, as the number is expected to be minimal and patients with contraindications in any case would not be treated with nintedanib.

## 6.3 STUDY POPULATION

### Indication

Patients to be recruited within this study have to have a physician diagnosed chronic fibrosing ILD with a progressive phenotype (except IPF), for which nintedanib is an indicated treatment.

Before visit 1, patients must not have been treated with either nintedanib or pirfenidone, i. e., all patients are considered treatment naïve with regard to these antifibrotic treatments.

- Only patients, for whom their treating physician has made the clinical decisions to start nintedanib treatment (but not actually started treatment) independently of this study, are eligible to enter the study.
- During the study, all patients are treated with nintedanib according to standard of care. For each individual patient, a treatment observation period of 52 weeks is aimed for. Patient's data with shorter observation period will be analyzed up to the date of data collection of the corresponding patient.

Inclusion and exclusion criteria are listed in section 9.2.2 of the Study Protocol as of 8 FEB 2021. Exclusion criterion 4 was changed in Local Amendment 1.0 dated 20 JAN 2022.

## 6.4 STUDY VISITS

In this NIS, data on the effect of a treatment with nintedanib on differences in cough and dyspnea scores, measured via the L-PF questionnaire, will be collected and this information will be assessed in relation to FVC from these patients' medical files in patients with chronic fibrosing ILD with a progressive phenotype.

Four visits are mandatory within this study. In addition to Visits 1, 3 and 5 optional study visits will be enabled. Each of these visits should take place not earlier than six weeks before and not later than six weeks after the planned visit date:

V1 – baseline visit

V3 – 26 weeks after V1 (20 – 32 weeks)

V5/V6 – 52 weeks after V1 (46 – 58 weeks)

Optional visits should take place:

V2 – 13 weeks after V1 (7 – 20 weeks)

V4 – 39 weeks after V1 (33 – 45 weeks)

If possible, patients who discontinue the study before week 52 for any reason should be contacted for survival status and follow-up data at week 52, as available (Visit 6).

The patients have the right to stop study participation any time and for any reason, without any drawback on their further treatment. Study participation may be stopped for a given patient in case of individual safety issues.

For more details on study visits please see section 9.2.3 of the Study Protocol.

## 7. VARIABLES

The following parameters will be collected and assessed at visits 1 to 5, as applicable:

- Patient demographics (age, gender, height, weight)
- Smoking history, current status (current smokers, former smokers, and never smokers) and pack-years
- History of ILD, including ILD entity and HRCT pattern (where available in patient documentation)
- current DLCO measures (where available in patient documentation)
- Concomitant diseases
- Previous ILD therapies in the 6 weeks before visit 1
- Current ILD related or other relevant concomitant medication
- FVC (mL and % pred.; if available in patient data)
- Severity of disease as per the treating physician's estimation (if available in patient data)
- L-PF questionnaire, completed by patient
- Safety: ADRs (serious and non-serious), fatal AEs, pregnancies during the study
- Rationale for treatment discontinuation (if applicable)
- Intention to continue or discontinue treatment with nintedanib (Ofev®) after the study (yes/no)
- Further treatment options yes/no, as applicable

### Living with pulmonary fibrosis questionnaire (L-PF)

The complete L-PF questionnaire is a 44 item questionnaire with two modules:

- 1) symptoms (23 items)
- 2) impacts (21 items)

The symptom module consists of three subdomains a) dyspnea b) cough c) fatigue. The impacts module yields a single impacts score. Symptoms and impacts scores are summed to yield a total L-PF score. The total and domain L-PF scores range from 0 to 100, the higher the score, the greater the impairment.

Scoring is performed as a summary score, the mean of the dimension ratings multiplied by 100. If the missing items are  $\geq 50\%$  within a score, then the corresponding score is set to missing. Each question is answered by the patient indicating one tick-box answer per question. Only one statement can be chosen.

## BOEHRINGER INGELHEIM Group of Companies

SEAP for BI Trial No: 1199-0449

Page 10 of 21

## Scoring of L-PF questionnaire [2]

Module	Domain	Scoring
Symptoms	Dyspnea items 1-12	
Items 1, 2, 4-10 and 12  If 'Yes' is ticked, scores range from 0 to 4.  If 'No' is ticked and A* is ticked, the score is 5.  If 'No' is ticked and B** is ticked, the item is not scored and does not contribute to the denominator.  If 'No' is ticked and neither A or B is ticked, the item is counted as missing but the item does contribute to the denominator.
 
Items 3, 11  Scores 0 to 4
 
Dyspnea Symptom Score = <math>\frac{\text{sum of items 1-12}}{\text{total score possible for items}} \times 100</math>

	Cough items 13-18	
Scores range from 0 to 4 for each item.
 
Cough Symptom Score = <math>\frac{\text{sum of items 13-18}}{24} \times 100</math>

	Energy items 19-23	
Items 19-23  Scores range from 0 to 4 for each item.
 
Item 23  If 'Yes' is ticked, scores range from 0 to 4.  If 'No' is ticked, the item is not scored and does not contribute to the denominator.
 
Energy Symptom Score = <math>\frac{\text{sum of items 19-23}}{\text{total score possible for items (20 or 16)}} \times 100</math>

Impact	Dyspnea items 1-6	
Scores range from 0 to 4 for each item.
 
Dyspnea Impact Score = <math>\frac{\text{sum of items 1-6}}{24} \times 100</math>

	Cough items 7-11	
Scores range from 0 to 4 for each item.
 
Cough Impact Score = <math>\frac{\text{sum of items 7-11}}{20} \times 100</math>

	Energy items 13-14	
Scores range from 0 to 4 for each item.
 
Energy Impact Score = <math>\frac{\text{sum of items 13-14}}{8} \times 100</math>

	Global items 12, 15-21	
Scores range from 0 to 4 for each item.
 
Global Impact Score = <math>\frac{\text{sum of items 12 and 15-21}}{32} \times 100</math>

\* Answer A: Patient avoided the activity because it was too difficult.

\*\* Answer B: Does not apply because the patient did not want to or had no opportunity to do the activity.

$$\text{Symptoms Total Score} = \frac{\text{sum of Dyspnea Symptom,Cough Symptom,Energy Symptom}}{3}$$

$$\text{Impacts Total Score} = \frac{\text{sum of Dyspnea Impact,Cough Impact,Energy Impact,Global Impact}}{4}$$

$$\text{Total L-PF Score} = \frac{\text{sum of Symptoms Total and Impacts Total}}{2}$$

**Overall survival (OS):** Overall survival of a patient is defined as the time from first dose of nintedanib until date of death. OS for patients who did not die will be censored at the date of last contact.

**Time to premature treatment discontinuation:** Time to premature treatment discontinuation is defined as the time from first dose of nintedanib until date of premature treatment discontinuation of nintedanib. The calculated time for patients without premature treatment discontinuation of nintedanib will be censored at the date of last contact.

**Time to first dose reduction:** Time to first dose reduction is defined as the time from first dose of nintedanib until the start date of first dose reduction to 100 mg/ twice daily or to other dose/ frequency excluding treatment interruption with 0 mg nintedanib administration daily. The calculated time for patients without dose reduction of nintedanib will be censored at the date of last contact.

**Time to first treatment interruption:** Time to first treatment interruption is defined as the time from first dose of nintedanib until the start date of first treatment interruption with 0 mg nintedanib administration daily. The calculated time for patients without treatment interruption of nintedanib will be censored at the date of last contact.

**Treatment-emergent adverse events (TEAE):** All adverse events occurring between start of treatment and end of the residual effect period will be considered 'treatment-emergent'. The residual effect period is defined as 28 days after the date of the last dose of study medication. Adverse events that start before first drug intake and deteriorate under treatment will also be considered 'treatment-emergent'.

**Change from baseline to week 52 in FVC [% pred.]:** FVC [% pred.] at week 52 – FVC [% pred.] at baseline

**Change from baseline to week 52 in FVC [mL]:** FVC [mL] at week 52 – FVC [mL] at baseline

**Change from baseline to week 52 in L-PF dyspnea symptom score:** L-PF dyspnea symptom score at week 52 – L-PF dyspnea symptom score at baseline

**Change from baseline to week 52 in L-PF cough symptom score:** L-PF cough symptom score at week 52 – L-PF cough symptom score at baseline

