**9.2.3      Study visits**

In this NIS, data on the effect of a treatment with nintedanib on differences in cough and dyspnea scores, measured via the L-PF questionnaire, will be collected and this information will be assessed in relation to FVC from these patients' medical files in patients with chronic fibrosing ILD with a progressive phenotype.

Four visits are mandatory within this study:

V1 – baseline visit

V3 – mid-observation period

planned visit date: 26 weeks after V1

must not take place earlier than week 20 or later than week 32 after V1

V5 – end of observation

planned visit date: 52 weeks after V1, must not take place earlier than week 46 or later than week 58 after V1

V6 – Follow-up 52 weeks after start of treatment

Each of these visit should take place not earlier than six weeks before and not later than six weeks after the planned visit date (V1 + 26 weeks; V1 + 52 weeks) and thus reflect patients' and physicians' real-world experience.

In addition to Visits 1, 3 and 5 described here, optional study visits will be enabled between V1 and V3 as well as between V3 and V5, each occurring about midway between V1 and V2 or V2 and V3, respectively. Optional visits should take place

optional Visit V2: planned visit date week 13 after V1

if applicable, V2 must not take place earlier than week 7 or later than week 20 after V1

optional visit V4: planned visit date week 39 after V1

if applicable V4 must not take place earlier than week 33 or later than week 45 after V1

When optional visits are conducted, then the same parameters as in Visit 3 should be documented.

Therefore, patients will be seen by their investigator at least every 6 months and up to every quarter of the observational period.

The baseline visit will take the patients ca. one hour including filling out the questionnaires, visits 2 to 6 will take about 30 minutes each. All data documented during those visits, including the questionnaires, record examinations and information necessary during the course of the disease and nintedanib treatment.

If possible, patients who discontinue the study before week 52 for any reason should be contacted for survival status and follow-up data at week 52, as available (Visit 6). A phone contact with the patient / relatives / family doctor is acceptable for V6.

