So, the time needed by the patient for the whole study depends on the number of visits performed. The duration of each visit depends on the amount of data to be collected and the possible questions to be discussed between investigator and participant. For baseline, we

presume about one hour, for the following visits about 30 minutes including filling out the questionnaire.

All details on the data collected and tasks performed at each visit are shown in [table 9.2.3: 1](#).

Table 9.2.3: 1 Flow Chart

Parameter	Visit 1; baseline visit	Visit 2; (optional) ca. week 13	Visit 3; mid of observa- tion; ca. week 26*	Visit 4; (optional) ca. week 39	Visit 5; end of observa- tion; ca. week 52	Visit 6 FU ca. week 52**
Informed Consent	X					
Inclusion / Exclusion Criteria	X					
Patient demographics (age, gender, height, and weight)	X					
Smoking history	X					
History of ILD, including ILD entity and HRCT pattern (where available in patient documentation)		X				
current DLCO measures (where available in patient documentation)	X	X	X	X	X	
Concomitant diseases / Comorbidities	X	X	X	X	X	
Past ILD therapies (6 weeks before visit 1)	X					
Current ILD related or other relevant concomitant medication	X	X	X	X	X	
FVC (mL and % pred.; if available in patient data)	X	X	X	X	X	X
Severity of disease as per the treating physician's estimation (if available in patient data)	X	X	X	X	X	X
L-PF questionnaire, completed by patient	X	X	X	X	X	X

Table 9.2.3: 1 (cont'd)

Flow Chart

Parameter	Visit 1; baseline visit	Visit 2; (optional) ca. week 13	Visit 3; mid of observa- tion; ca. week 26*	Visit 4; (optional) ca. week 39	Visit 5; end of observa- tion; ca. week 52	Visit 6 FU ca. week 52**
Safety: Adverse Drug Reactions (serious and non-serious), fatal AEs, pregnancy	X	X	X	X	X	X
Rationale for treatment discontinuation (if applicable)		X	X	X	X	
Further treatment options yes/no (as applicable)		X	X	X	X	X
Intention to continue or discontinue treatment with nintedanib after the study (yes/no)		X	X	X	X	
Survival data						X

\* after 26 weeks of observation for each individual patient

\*\* if available and/or patients willing to perform, phone contact acceptable

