### 10.3 Safety Analysis

All adverse drug reactions (ADRs) (serious and non-serious) and all AEs with fatal outcome as collected per study protocol will be included and summarized in the final study report. Separate tables will be provided for patients with serious adverse events.

Adverse events will be coded using the Medical Dictionary for Regulatory Activities (MedDRA) coding dictionary. Standard BI summary tables and listings will be produced. All treated patients will be included in the safety analysis. In general, safety analyses will be descriptive in nature and will be based on BI standards. All analyses will be based on the number of patients with AEs and not on the number of events. No hypothesis testing is planned.

Kaplan-Meier plots will be produced for the time to premature treatment discontinuation, for the time to first dose reduction and for the time to first treatment interruption.

Statistical analysis and reporting of adverse events will concentrate on treatment-emergent adverse events (TEAE).

Frequency, severity, and causal relationship of adverse events will be tabulated by system organ class (SOC) and preferred term (PT) after coding according to the current version of MedDRA.

Adverse events relating to gastrointestinal perforation and hepatic injury will be considered as adverse event of special interest (AESI) and will be tabulated separately.

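### Censoring the three tolerability curves at last contact counts time with unknown drug status as event-free and ties the dose-reduction estimate to week-52 contact success

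*SAP*

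**What the plan says.** SAP section 7 (definitions after the L-PF scoring table) starts all three clocks at first dose and ends them, for patients without the event, at last contact:

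- Premature discontinuation: "The calculated time for patients without premature treatment discontinuation of nintedanib will be censored at the date of last contact". The event is the stop itself; time runs "until date of premature treatment discontinuation of nintedanib".
- First dose reduction: "The calculated time for patients without dose reduction of nintedanib will be censored at the date of last contact".
- First interruption: "The calculated time for patients without treatment interruption of nintedanib will be censored at the date of last contact". The event is "the start date of first treatment interruption with 0 mg nintedanib administration daily"; the SAP does not say whether a permanent stop also counts.

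Overall survival has the same censoring date. Last contact is not defined. SAP 10.3 plans Kaplan-Meier plots of all three endpoints and describes the safety analysis as descriptive, without hypothesis testing.

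Protocol 9.2.3 asks that patients who leave before week 52 be contacted at week 52 (V6) if possible, for survival and follow-up data: "A phone contact with the patient / relatives / family doctor is acceptable for V6". In Table 9.2.3:1 the row "Rationale for treatment discontinuation (if applicable" is ticked for V2 to V5 but not V6. Concomitant medication and intention to continue nintedanib are also unticked at V6.

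**The concern.** Last contact suits survival, because a telephone call can establish that a patient is alive. It does not establish whether the patient was still taking nintedanib, or at what dose. Two illustrative patients show the effect:

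- One leaves the study on drug at week 10, and a relative reports survival at week 52. The rule credits 42 weeks free of discontinuation, reduction and interruption, although the flow chart lists no item recording dosing in that time.
- One stops nintedanib for good at week 8 without a prior reduction and is reached at week 52. This patient stays at risk of a first dose reduction for 44 weeks in which none can occur. If the call fails, the same patient is censored months earlier.

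The first is a bias. In the second, the quantity being estimated changes with the success of follow-up. Protocol 9.2.3 makes the V6 contact conditional on feasibility, and Protocol 10.1 makes it depend, for patients who withdraw, on their agreement. These three plots are the planned time-to-event summaries of tolerability, so a reader could take a follow-up artefact for a tolerability result.

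**Working it through.** The documents give no event rate for these endpoints, so there is no figure of theirs to reproduce. All rates below are assumptions. Hazards are constant over 52 weeks (scaled to 1), and patients who leave have the same hazards as those who stay.

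Notation: q = 52-week on-drug risk of dose reduction, d = risk of permanent stop, w = risk of leaving the study on drug; λ = −ln(1−q), μ = −ln(1−d), ω = −ln(1−w).

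**1. Unknown drug status, discontinuation endpoint.** Leavers are reached at week 52 for survival only, and later stops are not captured. Expected 1−KM = μ/(μ+ω) × (1 − e^−(μ+ω)). With d = 0.35, μ = 0.4308:

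- w = 0.05: ω = 0.0513; 0.8936 × 0.3825 = 0.342.
- w = 0.15: ω = 0.1625; 0.7261 × 0.4475 = 0.325.

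A true 35% reads 34.2% to 32.5%, a gap of 0.8 to 2.5 points. For d from 15% to 40% and w from 5% to 15%, the gap is 0.4 to 2.8 points.

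**2. Permanent stoppers, dose-reduction endpoint.** Let f be the share of stoppers reached at week 52; the others are censored when they stop. With s = λ+μ and a = fμ/s, expected 1−KM = 1 − [a + (1−a)e^−s]^(λ/(s(1−a))). With q = 0.30 and d = 0.25: λ = 0.3567, μ = 0.2877, s = 0.6444, e^−s = 0.525.

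- f = 0: 1 − e^−λ = 0.300.
- f = 0.5: a = 0.2232; 1 − 0.6310^0.7126 = 0.280.
- f = 1: a = 0.4465, exponent 1; 1 − 0.7371 = 0.263.

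Identical reduction and stopping histories therefore read 30.0%, 28.0% or 26.3%. For q from 20% to 40% and d from 15% to 40%, the distance between none and all reached is 1.5 to 8.0 points. The same holds for interruption only if a permanent stop is not counted as one.

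**3. Is 26.3% wrong?** The cumulative incidence of reduction with permanent stop as a competing event is λ/s × (1 − e^−s) = 0.5535 × 0.475 = 0.263, the same number. It is the share of all treated patients who have a reduction on drug. The 30.0% is the on-treatment risk. Each is legitimate; the rule as written fixes neither.

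**4. Unknown status against the competing-risk target.** Add leavers on drug to case 2, all reached: λ/(λ+μ+ω) × (1 − e^−(λ+μ+ω)).

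- w = 0.05: 0.5127 × 0.5013 = 0.257.
- w = 0.15: 0.4420 × 0.5538 = 0.245.

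Unknown-status time therefore lowers this target too, from 26.3% to 25.7-24.5%.

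**The case against.** A reader might infer that off-drug time inflates event-free time in all three curves and that tolerability always looks too good. The documents do not support that reading.

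- A recorded stop is itself the discontinuation event, so time after it cannot enter that curve. Only unknown-status time can.
- If a permanent stop is coded as a 0 mg period, it is also an interruption event. The SAP leaves this open.
- For dose reduction, keeping stoppers at risk to week 52 gives the competing-risk figure. It is low only against an on-treatment risk. Where stoppers are not reached, the rule reads above the competing-risk figure, so the direction is not fixed.

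These three limits stand.

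It can also be said that drug status may be known after all. Protocol 9.3.1 requires every reduction and interruption to be documented in the eCRF, V6 ticks safety and further treatment options, and neither the eCRF nor the separate technical SAP is available here. This means one cannot assert that status is never recorded. It does not rescue the rule: a last contact made only for survival would still end the clock. Patients who complete the study have V5 and V6 together, so for them no gap arises.

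Finally, the effect is small. With 100 patients, the standard error at 30% is √(0.3 × 0.7/100) = 4.6 points, larger than the 3.7-point shift in the middle case. Adverse events are also tabulated by frequency, severity and causality. This limits the importance of the point but does not justify leaving the estimand undefined.

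**Conclusion.** The point holds in two parts. First, for all three endpoints, time after the last documented drug status counts as event-free and biases cumulative event estimates downward, by 0.4 to 2.8 points for discontinuation under the assumed rates. Second, the dose-reduction estimate moves with the success of the week-52 contact, from 30.0% to 26.3% in the middle case. The same applies to interruption if a permanent stop is not one. The second part is a shifting estimand, not a bias of known sign.

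The sizes rest on constant hazards, equal hazards in leavers and stayers, and assumed event, stopping and leaving rates. Both effects vanish if last contact coincides with the last documented drug status. The plots are descriptive and the primary correlations are not touched. The change is worth making because it is cheap: the SAP already needs a last-dose date for its 28-day residual effect period.

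**What to change.** In SAP section 7:

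- Define last contact and keep it as the censoring date for overall survival only.
- Censor the three tolerability endpoints at the last date on which nintedanib status or dosing was documented.
- Show first dose reduction and first interruption as cumulative incidence with permanent discontinuation and death as competing events.
- State whether a permanent stop counts as an interruption.

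A nintedanib-status item with stop date at V6 would help but is optional. SAP version 3.0 is dated November 2022 and data collection was planned to end in February 2023, so it would be a late change.

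The cost is a few SAP sentences, a matching change in SAP 10.3, and a standard cumulative-incidence program. The reported figures may move slightly in either direction.
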